5.7.2 Contraception

Pembrolizumab may have adverse effects on a fetus in utero. Furthermore, it is not known if pembrolizumab has transient adverse effects on the composition of sperm. Non-pregnant, non-breast-feeding women may be enrolled if they are willing to use 2 methods of birth control or are considered highly unlikely to conceive. Highly unlikely to conceive is defined as 1) surgically sterilized, or 2) postmenopausal (a woman who is ≥ 45 years of age and has not had menses for greater than 1 year will be considered postmenopausal), or 3) not heterosexually active for the duration of the study. The two birth control methods can be either two barrier methods or a barrier method plus a hormonal method to prevent pregnancy. Subjects should start using birth control from study Visit 1 throughout the study period up to 120 days after the last dose of study therapy.

The following are considered adequate barrier methods of contraception: diaphragm, condom (by the partner), copper intrauterine device, sponge, or spermicide. Appropriate hormonal contraceptives will include any registered and marketed contraceptive agent that contains an estrogen and/or a progestational agent (including oral, subcutaneous, intrauterine, or intramuscular agents).

Subjects should be informed that taking the study medication may involve unknown risks to the fetus (unborn baby) if pregnancy were to occur during the study. In order to

participate in the study they must adhere to the contraception requirement (described above) for the duration of the study and during the follow-up period defined in section 7.2.2-Reporting of Pregnancy and Lactation to the Sponsor and to Merck. If there is any question that a subject will not reliably comply with the requirements for contraception, that subject should not be entered into the study.

5.7.3 Use in Pregnancy

If a subject inadvertently becomes pregnant while on treatment with pembrolizumab, the subject will immediately be removed from the study. The site will contact the subject at least monthly and document the subject's status until the pregnancy has been completed or terminated. The outcome of the pregnancy will be reported to the Sponsor and to Merck without delay and within 24 hours to the Sponsor and within 2 working days to Merck if the outcome is a serious adverse experience (e.g., death, abortion, congenital anomaly, or other disabling or life-threatening complication to the mother or newborn).

The study investigator will make every effort to obtain permission to follow the outcome of the pregnancy and report the condition of the fetus or newborn to the Sponsor. If a male subject impregnates his female partner the study personnel at the site must be informed immediately and the pregnancy reported to the Sponsor and to Merck and followed as described above and in Section 7.2.2.

5.7.4 Use in Nursing Women

It is unknown whether pembrolizumab is excreted in human milk. Since many drugs are excreted in human milk, and because of the potential for serious adverse reactions in the nursing infant, subjects who are breast-feeding are not eligible for enrollment.

5.8 Subject Withdrawal/Discontinuation Criteria

Subjects may withdraw consent at any time for any reason or be dropped from the trial at the discretion of the investigator should any untoward effect occur. In addition, a subject may be withdrawn by the investigator or the Sponsor if enrollment into the trial is inappropriate, the trial plan is violated, or for administrative and/or other safety reasons. Specific details regarding discontinuation or withdrawal are provided in Section 7.1.4 – Other Procedures.

A subject must be discontinued from the trial for any of the following reasons:

- The subject or legal representative (such as a parent or legal guardian) withdraws consent.
- Confirmed radiographic disease progression
Note: For unconfirmed radiographic disease progression, please see Section 5.2.2
- Unacceptable adverse experiences as described in Section 5.2.1.2
- Intercurrent illness that prevents further administration of treatment
- Investigator's decision to withdraw the subject
- The subject has a confirmed positive serum pregnancy test
- Noncompliance with trial treatment or procedure requirements

- The subject is lost to follow-up
- Administrative reasons

The End of Treatment and Follow-up visit procedures are listed in Section 6 (Protocol Flow Chart) and Section 7.1.5 (Visit Requirements). After the end of treatment, each subject will be followed for 30 days for adverse event monitoring (serious adverse events will be collected for 90 days after the end of treatment as described in Section 7.2.3.1). Subjects who discontinue for reasons other than progressive disease will have post-treatment follow-up for disease status until disease progression, initiating a non-study cancer treatment, withdrawing consent or becoming lost to follow-up. After documented disease progression each subject will be followed by telephone for overall survival until death, withdrawal of consent, or the end of the study, whichever occurs first.

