2.1.1.1 Definition of Dose-Limiting Toxicities

All toxicities will be graded using National Cancer Institute (NCI) CTCAE Version 4.0 (see Appendix).

Dose limiting toxicity (DLT) is defined as the appearance of side effects during treatment that are severe enough to prevent continuation of planned treatment. Dose limiting toxicity is defined as grade 3 or 4 non-hematologic toxicities that is definitely, probably, or possibly related to study drug, excluding alopecia, nausea or vomiting, grade 3 tumor flare, rash, mucositis, radiation dermatitis, need for feeding tube, and grade 3 immune-related events that resolve to grade 1 or less within 28 days. However, Grade ≥ 3 immune-mediated adverse events that include pneumonitis, renal failure nephritis, and elevation of AST, ALT, or bilirubin (with an exception for patients with liver metastases with baseline Grade 2 AST or ALT) should result in discontinuation of pembrolizumab and will be considered DLT (please see Table 3 for details on dose modification) .

In addition, adverse effects that are considered secondary to cisplatin or radiation are not considered DLT (see sections 5.2.1.3 and 5.2.2.7) unless they develop after first dose of pembrolizumab and prior to initiation of cisplatin and radiation. Cisplatin or radiation adverse effects include (but are not limited to):

- Grade 3 or 4 renal impairment (with the exception of renal failure or nephritis determined to be immune-related, which will be considered a DLT).
- Grade 2-4 neurotoxicity including ototoxicity (with the exception of myasthenia gravis and Guillain-Barre syndrome, which will be considered a DLT).
- Grade 3 or 4 mucositis
- Grade 3 or 4 myelosuppression

Although the above should result in dose modifications or delays as stated in section 5.2.1.3, they will NOT be considered DLTs for pembrolizumab on this study, and will NOT interfere with expansion to phase II portion of study.

If a patient is taken off study due to the above and has not yet reached evaluation for toxicity attributed to pembrolizumab, that subject will be replaced with another patient on study.

Non hematologic toxicities that will be attributed to pembrolizumab include:

- Grade 3-4 Pneumonitis
- Grade 3-4 diarrhea/colitis
- Grade 3-4 hyperglycemia
- Grade 3-4 hypophysitis
- Grade 3-4 thyroid dysfunction (hypothyroid or hyperthyroid)
- Grade 3-4 hepatic failure (elevation of AST, ALT, Bilirubin)
- Grade 5 toxicity

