5.2 Trial Treatments

The treatment to be used in this trial is outlined below in Table 2

Table 2 Trial Treatments

Drug	Dose/Potency	Dose Frequency	Route of Administration	Regimen/Treatment Period	Use
pembrolizumab	200 mg	Q3W	IV infusion	Starting 3W (-1 w) prior to chemotherapy, then Day 1 of each 3 week cycle Maximum 4 doses	Experimental
cisplatin	100 mg /m ²	Q3W	IV infusion	Day 1 of each 3 week cycle Maximum 3 dose	Standard
radiation	70 Gy/35fx	5 days /W	radiation	7 weeks	Standard

Trial treatment should begin on the day of randomization or as close as possible to the date on which treatment is allocated/assigned.

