5.2.1.2 Dose Modification for Pembrolizumab

Adverse events (both non-serious and serious) associated with pembrolizumab exposure may represent an immunologic etiology. These adverse events may occur shortly after the first dose or several months after the last dose of treatment. Pembrolizumab must be withheld for drug-related toxicities and severe or life-threatening AEs as per Table 3 below. See Section 5.6.1 and Events of Clinical Interest Guidance Document for supportive care guidelines, including use of corticosteroids.

Table 3
Dose Modification Guidelines for Pembrolizumab-Related Adverse Events

Toxicity	Hold Treatment For Grade	Timing for Restarting Treatment	Discontinue Subject
Diarrhea/Colitis	2-3	Toxicity resolves to Grade 0-1.	Toxicity does not resolve within 6 weeks of last dose or inability to reduce corticosteroid to 10 mg or less of prednisone or equivalent per day within 6 weeks.
	4	Permanently discontinue	Permanently discontinue
AST, ALT, or Increased Bilirubin	2	Toxicity resolves to Grade 0-1	Toxicity does not resolve within 6 weeks of last dose.
	3-4	Permanently discontinue (see exception below) ¹	Permanently discontinue
Type 1 diabetes mellitus (if new onset) or Hyperglycemia	T1DM or 3-4	Hold pembrolizumab for new onset Type 1 diabetes mellitus or Grade 3-4 hyperglycemia associated with evidence of beta cell failure.	Resume pembrolizumab when patients are clinically and metabolically stable.
Hypophysitis	2-3	Toxicity resolves to Grade 0-1	Toxicity does not resolve within 6 weeks of last dose or inability to reduce corticosteroid to 10 mg or less of prednisone or equivalent per day within 6 weeks.
	4	Permanently discontinue	Permanently discontinue
Hyperthyroidism	3	Toxicity resolves to Grade 0-1	Toxicity does not resolve within 6 weeks of last dose or inability to reduce corticosteroid to 10 mg or less of prednisone or equivalent per day within 6 weeks.
	4	Permanently discontinue	Permanently discontinue
Hypothyroidism	2-4	Therapy with pembrolizumab can be continued while treatment for the thyroid disorder is instituted	Therapy with pembrolizumab can be continued while treatment for the thyroid disorder is instituted.

Toxicity	Hold Treatment For Grade	Timing for Restarting Treatment	Discontinue Subject
Infusion Reaction	3-4	Permanently discontinue	Permanently discontinue

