Grade 2 Requires infusion interruption but responds promptly to symptomatic treatment (e.g., antihistamines, NSAIDS, narcotics, IV fluids); prophylactic medications indicated for < =24 hrs	Stop infusion and monitor symptoms. Additional appropriate medical therapy may include but is not limited to: IV fluids Antihistamines NSAIDS Acetaminophen Narcotics Increase monitoring of vital signs as medically indicated until the subject is deemed medically stable in the opinion of the investigator. If symptoms resolve within one hour of stopping drug infusion, the infusion may be restarted at 50% of the original infusion rate (e.g.,	Subject may be premedicated 1.5h (\pm 30 minutes) prior to infusion of pembrolizumab (MK-3475) with: Diphenhydramine 50 mg po (or equivalent dose of antihistamine). Acetaminophen 500-1000 mg po (or equivalent dose of antipyretic).

NCI CTCAE Grade	Treatment	Premedication at subsequent dosing
	
from 100 mL/hr to 50 mL/hr). Otherwise dosing will be held until symptoms resolve and the subject should be premedicated for the next scheduled dose.
 
Subjects who develop Grade 2 toxicity despite adequate premedication should be permanently discontinued from further trial treatment administration.
	

Grades 3 or 4 Grade 3: Prolonged (i.e., not rapidly responsive to symptomatic medication and/or brief interruption of infusion); recurrence of symptoms following initial improvement; hospitalization indicated for other clinical sequelae (e.g., renal impairment, pulmonary infiltrates) Grade 4: Life-threatening; pressor or ventilatory support indicated
	
Stop Infusion. Additional appropriate medical therapy may include but is not limited to:
 
 IV fluids Antihistamines NSAIDS Acetaminophen Narcotics Oxygen Pressors Corticosteroids Epinephrine 
Increase monitoring of vital signs as medically indicated until the subject is deemed medically stable in the opinion of the investigator. Hospitalization may be indicated.
 
Subject is permanently discontinued from further trial treatment administration.
	
No subsequent dosing

Appropriate resuscitation equipment should be available in the room and a physician readily available during the period of drug administration.
		

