6.0 TRIAL FLOW CHART

6.1 Study Flow Chart

Trial Period:	Screening Phase	Treatment Cycles				End of Treatment		Post-Treatment	Post Progression or new anti-cancer Therapy
						Discon	Safety Follow-up		
Treatment cycle/Title:	Main Study Screening Visit	C1 D-21	C1 D1	C1 D2 2	C1 D43	At time of Discon	30 days post discon	Every 12 weeks(± 1 w)	Every 12 weeks (±1 w)
Scheduling Window (Days):	-28 to -1	- 21 to - 14	± 2	± 2	± 2				
Informed Consent	x								
Inclusion/Exclusion Criteria	x								
Standard Chemotherapy Administered Cisplatin-100 mg			x	x	x				
Trial Treatment Administration Pembrolizumab 200 mg		x	x €	x €	x €				
Radiation- 70Gy/35 fx			x Δ	x Δ	x Δ				
Survival Status								x	x [∞]
Review Adverse Events		x	x	x	x	x	x	x €	

Trial Period:	Screening Phase	Treatment Cycles				End of Treatment		Post-Treatm ent	Post Progression or new anti-cancer Therapy
						Discon	Safety Follow-up	Follow-Up	Survival Follow-Up Phase
Treatment cycle/Title:	Main Study Screening Visit	C1 D-21	C1 D1	C1 D2 2	C1 D43	At time of Discon	30 days post discon	Every 12 weeks(± 1 w)	Every 12 weeks (±1 w)
Scheduling Window (Days):	-28 to -1	- 21 to - 14	± 2	± 2	± 2				
Directed Physical Examination		X	X	X	X	X		x¥	
Full Physical Exam	X								
Review of Concomitant Medications	X	X	X	X	X	X	X	X	
Review Medical History	X								
Subsequent Anti-Cancer Therapy Status							X		
Endoscopic Examination in Office	xç		xç					x£	
Vital Signs and Weight	x	x	x	x	x	x			
Review Speech/swallow questionnaire ç	x							x¥	
Review Nutrition questionnaire ç	x							x¥	

Trial Period:	Screening Phase	Treatment Cycles				End of Treatment		Post-Treatment Follow-Up	Post Progression or new anti-cancer Therapy
						Discon	Safety Follow-up		
Treatment cycle/Title:	Main Study Screening Visit	C1 D-21	C1 D1	C1 D2 2	C1 D43	At time of Discon	30 days post discon	Every 12 weeks(± 1 w)	Survival Follow-Up Phase Every 12 weeks (±1 w)
Scheduling Window (Days):	-28 to -1	-21 to -14	± 2	± 2	± 2				
ECOG Performance Status	x	x	x	x	x	x			
Functional Oral Intake ϕ	X							x \neq	
Pregnancy Test – Urine or Serum b-HCG if appropriate	x								
CBC with Differential	x	x	x	x	x				
Comprehensive Serum Chemistry Panel	x	x	x	x	x				
T3, FT4 and TSH	x		x		x				
Tumor Imaging (PET preferred)	x							x \neq	
Archival or Newly Obtained Tissue Collection	x		x ϕ						

Trial Period:	Screening Phase	Treatment Cycles				End of Treatment		Post-Treatment	Post Progression or new anti-cancer Therapy
						Discon	Safety Follow-up		

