7.1.5.3 Post-Treatment Visits

7.1.5.3.1 Safety Follow-Up Visit

The mandatory Safety Follow-Up Visit should be conducted approximately 30 days after the last dose of trial treatment or before the initiation of a new anti-cancer treatment, whichever comes first. All AEs that occur prior to the Safety Follow-Up Visit should be recorded.

Subjects with an AE of Grade > 1 will be followed until the resolution of the AE to Grade 0-1 or until the beginning of a new anti-neoplastic therapy, whichever occurs first. SAEs that occur within 90 days of the end of treatment or before initiation of a new anti-cancer treatment should also be followed and recorded.

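### The plan is inconsistent about what stops after pembrolizumab toxicity, and does not name the treatment component that starts the 30-day AE and 90-day SAE windows

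*Combined protocol and SAP*

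**What the plan says.** **What stops.**

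- Section 2.1.1.1: grade 3 or higher immune-mediated pneumonitis, renal failure or nephritis, and hepatic enzyme or bilirubin elevation "should result in discontinuation of pembrolizumab and will be considered DLT".
- Section 5.2.1.2: "Pembrolizumab must be withheld for drug-related toxicities and severe or life-threatening AEs as per Table 3 below". Table 3 says when to discontinue permanently, but its last column is headed by the subject and not the drug.
- Section 5.2.1.4: a pembrolizumab delay of more than 6 weeks ends pembrolizumab. Later in the same paragraph, failure to recover after a 6-week delay ends study treatment, subject to an individual exception.
- Section 5.6.1, Table 4, grade 3–4 infusion reaction: "Subject is permanently discontinued from further trial treatment administration".
- Section 5.8: "A subject must be discontinued from the trial for any of the following reasons", and one listed reason is "Unacceptable adverse experiences as described in Section 5.2.1.2".
- Section 5.9: after a DLT, study therapy may be stopped by agreement, or doses may be modified under 5.2.1 and therapy continued.

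**What trial treatment means.** Section 5.2 states "The treatment to be used in this trial is outlined below in Table 2", and that table lists pembrolizumab, cisplatin and radiation. The flow chart in 6.1 has a row "Trial Treatment Administration Pembrolizumab 200 mg", with separate rows for cisplatin and radiation.

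**When the safety windows start.** The safety visit in 7.1.5.3.1 falls "approximately 30 days after the last dose of trial treatment". Sections 7.2 (AEs, 30 days) and 7.2.3.1 (SAEs, 90 days) count from cessation of treatment. None of the three names a component. The imaging visit in 7.1.5.4 does: it counts from the last radiation or drug therapy.

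**The concern.** Take a patient with grade 3 hepatic toxicity after the lead-in dose. A site following 2.1.1.1 stops one drug. A site following 5.8 to the letter removes the patient from the trial. A site following 5.9 may continue modified therapy. The cisplatin rules in 5.2.1.3 repeatedly say that radiation goes on when cisplatin is held. No corresponding sentence covers cisplatin and radiation once pembrolizumab is permanently stopped. These patients are treated for cure and the primary endpoint is 18-month laryngectomy-free survival, so the sites' actions should not depend on which section they read.

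The same loose terms start the safety windows. If the start is the last pembrolizumab dose, the windows close earliest in the patients who stopped pembrolizumab for toxicity. The safety of this combination is what the run-in was set up to learn, since 2.1 says it has not been described before.

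**Working it through.** No stated figure has to be reproduced. The check compares the rules and then does calendar arithmetic on the plan's own schedule.

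**1. Comparison of the rules**

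- *Grade 3 hepatic toxicity.* The object stopped is pembrolizumab in 2.1.1.1 and the trial in 5.8. In 5.9 stopping is optional.
- *Grade 3–4 infusion reaction.* Table 3 calls for permanent discontinuation in the pembrolizumab section, and Table 4 stops trial treatment.
- *Six-week delay.* The object is pembrolizumab in one sentence of 5.2.1.4 and study treatment in a later one. The cisplatin limit in that paragraph is 3 weeks, so both sentences most naturally refer to the pembrolizumab limit.

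**2. Inputs for the windows**

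- Lead-in L from first pembrolizumab to start of radiation: 21 days, minimum 14 (5.2.1.4).
- Radiation: 35 fractions, 5 per week, starting Monday, Tuesday or Wednesday (Table 2, 5.2.2.1).
- Window length W: 30 or 90 days.

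**3. Last fraction.** Let R be the days from the first to the last fraction, without breaks. A Monday start ends on the Friday of week 7: R = 6×7 + 4 = 46. A Tuesday or Wednesday start ends one day short of 7 full weeks: R = 7×7 − 1 = 48. Counting the first fraction as day 1, the last falls on day 47 or 49.

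**4. Worst case: lead-in dose only, chemoradiation completed.** Counted from the start of radiation, the window ends at W − L on a pembrolizumab clock and at R + W on a last-fraction clock. The difference is R + L for any W.

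- 30 days: 30 − 21 = 9 to 30 − 14 = 16, against 46 + 30 = 76 to 48 + 30 = 78.
- 90 days: 90 − 21 = 69 to 90 − 14 = 76, against 46 + 90 = 136 to 48 + 90 = 138.
- Difference: 46 + 14 = 60 to 48 + 21 = 69 days.
- On the pembrolizumab clock the SAE window closes 90 − L − R days after the last fraction: 90 − 21 − 48 = 21 to 90 − 14 − 46 = 30.

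Ten missed treatment days add two calendar weeks, so R = 60 to 62. The difference becomes 60 + 14 = 74 to 62 + 21 = 83 days, and the SAE window closes 90 − 21 − 62 = 7 to 90 − 14 − 60 = 16 days after the last fraction.

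**5. Later stops (21-day lead-in, no breaks).** If the last pembrolizumab dose is d days after radiation starts, the gap is R − d.

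- After D1 (d = 0): 46–48 days.
- After D22 (d = 21): 25–27 days.
- After D43 (d = 42): 4–6 days.

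With a 14-day lead-in, the 21-day spacing of pembrolizumab puts the second and third doses about a week after D1 and D22. The first two gaps then become about 39–41 and 18–20 days.

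**The case against.** The strongest reply is that, read in context, most of this resolves itself.

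- *Each component has its own rules.* Section 5.2.1.3 item 8 holds cisplatin for other grade 3–4 events until recovery, and 5.2.2.6 limits radiation breaks to severe acute toxicity or intercurrent illness. This stands: a reader might infer that nothing governs cisplatin and radiation after pembrolizumab toxicity, and that is not so. What is missing is the linking statement for permanent discontinuation.
- *Table 4 is about pembrolizumab.* It is introduced for reactions to pembrolizumab. Reading it as an instruction to stop radiation means importing the Table 2 meaning into it. This largely stands, but the documents supply both meanings of the term.
- *Section 5.9 defers to 5.2.1.* True, so it adds no new dosing rule. It still permits continued therapy where 5.8 mandates leaving the trial.
- *Follow-up continues anyway.* Sections 5.8, 7.1.5.4 and 2.1.2 keep patients in disease-status follow-up, 12-weekly examination and two years of laryngectomy and survival follow-up. Discontinuation from the trial in 5.8 may therefore mean end of treatment, but 5.8 does not say so.
- *Safety data are caught elsewhere.* Section 7.1.2.1 records AEs throughout the study and follow-up, 7.2 adds recording at each examination, and the flow chart reviews AEs at D1, D22 and D43. Section 7.2.3.1 requires SAEs considered related to the Merck product to be reported whenever they come to light. This stands, and it removes most of the AE loss and the loss of pembrolizumab-related SAEs.
- *The last-fraction clock is the more natural reading.* The flow chart places the discontinuation and 30-day visits after D43, and its 12–16 weeks from end of treatment match the 14 ± 2 weeks from completion of radiation in 2.1.2. That is a fair inference, but the safety sections do not state it.

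**Conclusion.** The inconsistency is real. After pembrolizumab toxicity the plan names, in different places, pembrolizumab, study treatment, trial treatment or trial participation as the thing that stops, and trial treatment has two meanings. No sentence says whether cisplatin and radiation continue once pembrolizumab is permanently stopped, and the 30-day and 90-day windows do not name the component that starts them.

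The effect on the windows is at most 60–69 days without radiation breaks, in a patient who received only the lead-in dose and completed chemoradiation. With D1, D22 and D43 dosing it falls to 46–48, 25–27 and 4–6 days for later stops. The loss falls mainly on SAEs judged unrelated to pembrolizumab. That category matters in a three-component regimen, because attribution is difficult and 7.2.3.1 collects SAEs regardless of it. The documents do not say how many patients would be affected.

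Two stronger readings are tempting. One is that the plan directs sites to abandon radiation or loses these patients for laryngectomy-free survival. The component-specific rules and the continued follow-up do not support that. The other is that SAEs after radiation go uncollected as a class. The rule on pembrolizumab-related SAEs contradicts that.

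**What to change.** 1. Reconcile 2.1.1.1, Table 3, 5.2.1.4, Table 4, 5.8 and 5.9 so that each stopping rule names the component or components it stops. State what then applies to the others. The clinical choice is the sponsor's.
2. In 5.8, separate discontinuation of pembrolizumab, of cisplatin and of radiation from withdrawal from the trial. State that a patient who stops a component stays in laryngectomy and survival follow-up.
3. Give trial treatment one meaning in Table 2 and the flow chart.
4. Start the discontinuation visit, the 30-day AE window and visit, and the 90-day SAE window at the last dose or fraction of any of the three components, as 7.1.5.4 already does for imaging.

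The cost is protocol wording, one flow-chart label and longer AE and SAE collection in patients who stop pembrolizumab early. For most stopping points that is a few weeks. In the worst case above it is 60–69 days, or 74–83 with ten missed treatment days.
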